- **Randomization:** Following enrollment and completion of baseline testing a randomization assignment will be generated by computer and block randomization will be performed within strata defined by sex. Participants will be randomized 1:1 to MORE or CON

INTERVENTION:

Group-Based Interventions

- **MORE:** Participants randomized to MORE will complete the previously developed 8-week, MORE program (E. Garland, 2013). MORE is delivered in a group format, consisting of 8 weekly HIPPA compliant virtual zoom 2-hour sessions. The MORE curriculum will be adapted for this intervention to address food intake behaviors and will provide training in mindfulness techniques to increase awareness of, and self-control over, cravings; reappraisal skills to promote emotion regulation and restructure motivations for highly palatable food intake; and savoring pleasant events and emotions to overcome defects in natural reward processing. In addition to class sessions, participants will complete daily, 15-minute, audio-guided mindfulness, reappraisal, and savoring sessions at home. The intervention will be delivered by a study team member who will receive training and supervision from [name]. Treatment fidelity will be monitored as in ongoing RCTs of MORE (E. L. Garland, Manusov, et al., 2014).
- **CON:** Participants randomized to the control intervention will complete an 8-week healthful lifestyle program via HIPPA compliant zoom sessions. The curriculum will be based on the Diabetes Prevention Program's Prevent T2 for Life program, which is an evidence-based national healthful lifestyle maintenance intervention. This program includes training in healthful eating, meal planning, and recipe modification; time and stress management; adapting lifestyle habits for continued success during holidays, vacations, and other special situations; and relapse prevention. CON will be virtually delivered by a study team member who will receive training and oversight from [name], who has delivered this intervention previously. In addition to class sessions, participants will be completed daily, 15-minute activities related to the course content (i.e. – designing a meal plan and grocery shopping list; creating a list of healthful take-out or restaurant meals; etc) at home. Time-in-treatment will be matched between conditions.

POST-INTERVENTION TESTING: Repeat baseline testing at the end of 8 weeks and at 6 months.

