OPTIONAL POST-INTERVENTION TESTING AT 1 YEAR: 6 months after the post-intervention testing time point participants will be contacted and asked to complete follow-up questionnaires. These questionnaires are designed to assess participants' perceptions of the intervention and if they achieved their weight-loss maintenance goals.

STOPPING PROCEDURES and ADVERSE EVENTS: Participants will be encouraged to report any adverse events that they believe may have been a result of the study.

Procedures performed for research purposes only:

Statistical Methods, Data Analysis and Interpretation

The statistical analysis plan presented below was developed in collaboration with [name] of the SDBC.

Aim 1 will focus on the efficacy of the intervention (MORE vs. CON) on the primary outcome of body mass and body composition at week 8 and week 24. We will first provide descriptive summaries of each variable measured at week 0 (baseline), week 8 and 24, as well as by intervention group. Linear mixed models (LMM) will then be used to relate weekly assessments of body mass from week 0 to week 24 to the intervention, controlling for covariates likely to be associated with the outcome. Specifically, this will include baseline body mass and composition, and other demographic covariates including (but not be limited to) age, sex, race and socioeconomic status. Different slopes for time trend and intervention-time interaction term will be assumed for the intervention period (week 0-8) and follow-up period (week 8-24). Random intercepts will be used to account for correlations on the participant level. An advantage of this approach is treatment effect estimates remain consistent and approximately unbiased if missing data follow a missing-at-random pattern (MAR; data values are independent of missingness mechanism conditional on the observed data), the most general data-centric missing data assumption. Secondary analyses will fit separate LMM models to assess changes in fat mass and lean mass measured at week 0, 8 and 24. Similarly, LMM will be fitted for each of the eating behaviors and energy intake outcome collected for **Aim 2** (detailed above), where skewed outcomes may be transformed to approximate normality. Bonferroni correction will be performed to adjust for multiple comparisons.

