Sample size, and power consideration: For a total of 100 participants randomized 1:1 to each study arm, we conservatively anticipate 20% attrition. This leaves us with complete data on n=80 participants total (n=40 per group). This provides $\geq 80\%$ power for detecting differences in body mass (or other outcomes assessed in Aim 1 and 2) by at least 0.89 standard deviations. We expect power will be greater for our primary analysis models when adjusting for covariates associated with outcomes. Although we will have limited statistical power for the current analysis this trial will generate the effect size necessary to power a future trial, while allowing us to collect outcome measures on a practical amount of participants within the 2-year award period.

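### The 0.89 SD detectable difference is given without alpha or divisor; it fits Bonferroni over about 20 tests that include body mass, and Holm would hold the same error rate with power never lower

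*Combined protocol and SAP*

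**What the plan says.** Under Sample size, and power consideration, the plan randomizes 100 participants 1:1, allows for 20% attrition, and so arrives at 40 per arm. It then claims at least 80% power for "detecting differences in body mass (or other outcomes assessed in Aim 1 and 2) by at least 0.89 standard deviations". One figure therefore serves body mass and every other Aim 1 and Aim 2 outcome. The section expects covariate adjustment to raise power in the primary models. It also concedes: "Although we will have limited statistical power for the current analysis this trial will generate the effect size necessary to power a future trial".

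The only text on error control closes the methods paragraph of Statistical Methods, Data Analysis and Interpretation, after the Aim 1 and Aim 2 models: "Bonferroni correction will be performed to adjust for multiple comparisons". It names no overall alpha, family or divisor, and it does not exempt body mass. Aim 1 is described there as addressing the "primary outcome of body mass and body composition at week 8 and week 24".

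**The concern.** The detectable difference does not follow from the inputs printed beside it. The same 40 per arm would detect a much smaller difference at the conventional two-sided 0.05. The gap points to a much stricter alpha that the plan does not write down.

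What is at stake is the primary comparison. If body mass shares its alpha equally with some 20 tests, much of the power for a moderate effect is lost. Sample size cannot recover it, because the Informed Consent section says enrollment ends as of March 2023. The analysis method is where something can still be gained.

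**Working it through.** **Inputs.** From the sample size section: 100 × 0.8 = 80, or 40 per arm (this reproduces); power at least 80%; difference 0.89 SD. Assumed because not stated: two-sided test, overall alpha 0.05, two-sample comparison of means with SD = 1.

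**Formulas.** Normal approximation: d = (z for 1 − α/2 + z for 0.80) × √(2/n). Exact: noncentral t with 2n − 2 = 78 degrees of freedom and noncentrality d × √(n/2), solved for d at 80% power.

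**Step 1: the plan's figure without correction.** Normal: (1.960 + 0.842) × √(2/40) = 2.802 × 0.2236 = 0.626 SD. The t-test gives 0.634 SD. Other uncorrected variants by t-test: one-sided 0.05 gives 0.56 SD, 90% power gives 0.73 SD, and 50 per arm gives 0.57 SD. None reaches 0.89. At 0.89 SD and two-sided 0.05, power is 97.6%.

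**Step 2: the alpha that 0.89 implies.** Solving the t-test for 80% power at 0.89 SD gives alpha = 0.00251, and 0.05/0.00251 = 19.9.

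| Divisor k | Detectable SD (t) |
|---|---|
| 1 | 0.634 |
| 2 | 0.701 |
| 14 | 0.863 |
| 19 | 0.887 |
| 20 | 0.890 |
| 21 | 0.894 |
| 26 | 0.910 |

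Divisors 19 to 21 round to 0.89. With the normal approximation the range is 28 to 31.

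**Step 3: whether the plan holds about 20 tests.** One count does: body, fat and lean mass (3), the three scales of the Three Factor Eating Questionnaire (3), diet self-efficacy (1), food cravings (1), free-living intake (1) and ad libitum intake (1) make 10 outcomes; at two time points that is 20 tests. It leaves out interoceptive awareness, savoring and the appetite ratings, all of which appear under Baseline Testing. Adding them gives 13 × 2 = 26 tests and 0.91 SD. The shorter list of four eating outcomes in Purpose and Objectives, plus the three mass measures, gives 7 × 2 = 14 tests and 0.86 SD. Twenty is a reconstruction that the documents do not confirm.

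**Step 4: power for body mass (unadjusted t-test, 40 per arm).**

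| True difference | alpha 0.05 | alpha 0.025 | alpha 0.0025 (k = 20) |
|---|---|---|---|
| 0.63 SD | 79.5% | 70.2% | 38.7% |
| 0.80 SD | 94.2% | 89.9% | 67.3% |
| 0.89 SD | 97.6% | 95.3% | 80.0% |

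**Step 5: Holm against Bonferroni.** Holm compares the smallest p-value with α/20, the next with α/19, and so on. No threshold is below α/20, so power cannot be lower. Simulated with 20 tests, 40 per arm, equal true effects, correlations 0, 0.3 and 0.6 (an assumed range) and 40,000 runs each, the power of one true test was:

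| Tests with a true effect | 0.634 SD: Bonferroni, Holm | 0.89 SD: Bonferroni, Holm |
|---|---|---|
| 1 of 20 | 39%, 39% | 80%, 80% |
| 10 of 20 | 39–40%, 42–43% | 80%, 83–84% |
| 20 of 20 | 39–40%, 47–50% | 80%, 90–95% |

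Simulated family-wise error under Holm was at most 0.049.

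**The case against.** The strongest reply is that nothing here is wrong. The power claim is true as worded, Bonferroni is valid, and the plan openly concedes limited power in a trial meant to supply an effect size. All of that stands. Holm corrects no error; it is a better use of the same error budget. Its gain for body mass is nil if body mass alone differs, and nothing in the documents supports the last row of the simulation, where all 20 tests share one effect. The power losses in Step 4 are for an unadjusted test, whereas the plan fits a covariate-adjusted mixed model to weekly body mass, so actual power should be higher at each alpha. The plan's purpose does not remove the point, because it still prescribes a corrected test of a primary outcome.

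Three stronger readings are tempting, and the documents do not support them.

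- A reader might infer that 0.89 is an arithmetic error or that the trial is undersized because of it. The figure is conservative at 0.05 and matches 0.05/20.
- A reader might infer that it came from about 21 per arm, or from variance doubled for group delivery. The first contradicts the stated 40 per arm. The second gives 0.897 by t-test, and although treatment is delivered in groups, the plan states no variance inflation and models correlation only within participants.
- A reader might infer that it is wholly unknown whether body mass is corrected. One detectable difference for body mass and all other outcomes, with a correction that exempts none, points to body mass being inside the family. What is missing is the explicit statement and the divisor.

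**Conclusion.** The point holds as a low-cost improvement. The plan's 0.89 SD most likely reflects Bonferroni over about 20 tests with body mass among them, but the plan does not say so. If that is right, the price for body mass is a detectable difference of 0.89 rather than 0.63 SD. This rests on an assumed two-sided overall alpha of 0.05, an assumed divisor of 20 and an unadjusted t-test at a single time point. The gain from Holm depends on how many other outcomes truly differ: at 0.634 SD, power rises from 39% to about 42% if half do.

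A separate minor clarification is that body composition is named with the primary outcome, while "Secondary analyses will fit separate LMM models to assess changes in fat mass and lean mass". That does not explain 0.89.

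**What to change.** 1. List the Aim 1 and Aim 2 tests that form the family, including how many concern body mass: the plan names two time points but also models separate slopes for two periods. Replace Bonferroni with Holm over that list. Record both before any comparison between arms is seen.
2. Beside the detectable difference, state the alpha, sidedness, test and divisor used. By t-test at 40 per arm and 80% power, the figure is about 0.89 SD if alpha is divided by about 20, 0.70 SD at 0.025 for each of two time points, and 0.63 SD at 0.05.

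Testing body mass outside the family at its own 5% is an option for the sponsor, not a correction; error across the two families could then reach 5% + 5% = 10%.

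The change needs no extra participants, visits or measurements. Its cost is the loss of the simple simultaneous confidence intervals that match Bonferroni. Unadjusted intervals can still be reported for planning the future trial.
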